8.3.2.9 Lymphocyte Proliferative Responses Stimulation Index (SI)

Lymphocyte proliferative response to PHA, Tetanus, and Candida were collected. Early in the study, these responses were provided by Quest laboratories. At a later date, these analyses were moved to the in-house immunogenetics laboratories at each study site. Since the results from the in-house laboratories are not comparable with those from Quest, they will be summarized separately.

The stimulation index will be calculated for each parameter as the sample response/control response. Stimulation indices will be summarized for the OTL-101 treated subjects by visit for each parameter, separately for the data from the Quest and in-house laboratories. In addition, for each parameter, the median and range will be plotted on a logarithmic scale over time. These stimulation indices will be compared with the normal reference ranges provided by the study sites and the number (%) of subjects with responses above and below the normal range will be summarized by visit as well as at any time post infusion.

8.3.2.10 Antibody Responses

Antibody responses to Tetanus and Polyribosylphosphate (PRP) were evaluated.

Final Version 4.0 Page 21 of 27

The response to each of the antibodies will be summarized for the OTL-101 treated subjects using descriptive statistics.

8.3.3 Additional Efficacy Endpoints

8.3.3.1 Use of PEG-ADA Enzyme Replacement Therapy

The time to withdrawal of PEG-ADA ERT will be calculated (in months) as: 12*(stop date of PEG-ADA ERT – date of transplant) /365.25, or, for HSCT control subjects for whom the dates were not recorded, as: age in months when PEG-ADA stopped – age in months at transplant.

Time to withdrawal of PEG-ADA ERT will be summarised for the OTL-101 treated and HSCT control groups using descriptive statistics and, if appropriate, estimated from a Kaplan-Meier curve in which subjects who are still receiving PEG-ADA ERT will be censored at the time of their last visit.

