nutritional support), consequences of toxicity to Busulfan, engraftment of transduced cells and immune reconstitution. Alternatively, for out of town subjects who are clinically stable, post-transplant care may be transferred to the home physician provided they have agreed to assume the post-transplant monitoring. The monitoring can take place as an in-patient or as an outpatient. In this case, the subject will stay a minimum of 3 days after infusion of the cells at the treatment facility (UCLA or NIH) prior to being transferred. This planned discharge and subsequent re-admission to a second facility would not constitute an adverse event.

PEG-ADA will be stopped on day +30 post-cell product infusion if the patient received busulfan and the final cell product and does not have active infections or other major medical problems.

For subjects who have slow recovery of counts after transplant (beyond Day +30), CBC/Diff will be performed at least once every 7-10 days, until ANC is >500 cells/mm³. If after day +42 the criteria for non-engraftment are met (persistent ANC $< 200/\mu\text{l}$ or platelets $< 20,000/\mu\text{l}$) after cell infusion on three independent and consecutive determinations over at least ten days, the back-up cells will be given. If hematologic reconstitution does not occur by Day +90 from the initial infusion of the cell product, prolonged unresponsive pancytopenia will exist.

Infection prophylaxis: The subjects will be maintained on prophylactic antibiotics and intravenous gamma-globulin replacement and will be closely monitored as an outpatient. They will be readmitted to a hospital when deemed clinically necessary. These reasons include, but are not limited to: fever and neutropenia, bacteremia, possible central venous access device infection, or other infections that require initial parenteral antibiotics, organ failure, extreme adverse social situations, and/or bleeding.

Prophylactic antibiotics will be used to provide coverage for *Pneumocystis jirovecii* pneumonia and mucosal yeast:

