8.2.16 Transplant Details for the HSCT Controls

Age (months) at transplant, number of CD34⁺ cells/kg transplanted and busulfan dose, if appropriate, will be summarized for each HSCT control group using descriptive statistics.

Final Version 4.0 Page 16 of 27

Number (%) of subjects with each type of transplant cells, transplant donor type, conditioning type, receiving enzyme replacement therapy (ERT) prior to the transplant, receiving ERT after the transplant, receiving IgRT prior to the transplant, receiving IgRT after the transplant and receiving gene therapy after the transplant will be summarized for each HSCT control group.

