8.3 Efficacy Evaluations

The primary comparison for all efficacy analyses will be between the OTL-101 treated subjects and the allogeneic HSCT controls treated at either GOSH or Duke University without a matched related donor.

Secondary comparisons will be between:

- the OTL-101 treated subjects and the HSCT controls treated at either GOSH or Duke University with a matched related donor;
- the OTL-101 treated subjects and the total group of HSCT controls.

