8.3.2.2 Use of Immunoglobulin Replacement Therapy

The number (%) of subjects receiving immunoglobulin replacement therapy (IgRT) will be summarised by visit for the OTL-101 treated subjects.

The time to cessation of IgRT will be calculated (in months) as:

12*(stopping date of IgRT – date of transplant) /365.25,

or, for HSCT control subjects for whom the dates were not recorded, as:

age in months when IgRT stopped – age in months at transplant.

Time to cessation of IgRT will be summarised for the OTL-101 treated and HSCT control groups using descriptive statistics and, if appropriate, estimated from a Kaplan-Meier curve in which subjects who are still receiving IgRT will be censored at the time of their last visit.

The number (%) of subjects who have stopped treatment with IgRT at 12, 18 and 24 months without restarting at any subsequent time point will be summarized for the OTL-101 treated and HSCT control groups (data permitting).

In addition, serum immunoglobulin levels (IgG, IgA and IgM) will be measured at each visit for the OTL-101 treated subjects. Levels of IgG, IgA and IgM and changes from baseline will be summarised by visit using descriptive statistics. In addition, plots of the median value and range over time on a logarithmic scale will be produced for each parameter along with individual plots for each subject which will include age-dependent normal ranges provided by the study sites.

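### SAP 8.3.3.1 summarises time to PEG-ADA stop for OTL-101 against HSCT controls, but for OTL-101 the stop is scheduled at day +30, and the formula has no rule for pre-transplant stops, never-users or restarts

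*SAP*

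**What the plan says.** SAP 8.3.3.1 is the only entry under the heading for additional efficacy endpoints. It defines time to PEG-ADA withdrawal as "12*(stop date of PEG-ADA ERT – date of transplant) /365.25" or, for controls without recorded dates, "age in months when PEG-ADA stopped – age in months at transplant". The output is a summary by group: "Time to withdrawal of PEG-ADA ERT will be summarised for the OTL-101 treated and HSCT control groups using descriptive statistics". A Kaplan-Meier curve is optional, and its one censoring rule is that "subjects who are still receiving PEG-ADA ERT will be censored at the time of their last visit". No test is named. The opening of SAP 8.3 sets the frame: "The primary comparison for all efficacy analyses will be between the OTL-101 treated subjects and the allogeneic HSCT controls".

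Protocol 7.4 fixes when the OTL-101 arm stops: "PEG-ADA will be stopped on day +30 post-cell product infusion if the patient received busulfan and the final cell product", provided the child has no active infection or other major medical problem. Protocol 6.4.1 repeats the rule. Protocol 2.3.1 explains that the stop belongs to the treatment plan and is meant to favour gene-modified cells; it also allows that some children may not be on PEG-ADA. The controls are a retrospective group under routine practice (Protocol Appendix H), and no stop day is given for them.

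SAP 8.2.16 tabulates controls "receiving enzyme replacement therapy (ERT) prior to the transplant, receiving ERT after the transplant" as separate items. SAP 8.3.1.2 counts PEG-ADA reinstitution as an event in event-free survival and also summarises time to each event type other than death.

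**The concern.** An efficacy time should depend on how well the treatment works. Here the OTL-101 time is set by the schedule, well before graft function is judged: the protocol's checks on ADA activity, T-cell recovery and gene marking that lead to a restart come at 6 months (Protocol 7.5) and 12 months (Protocol 6.4.1). The control time, if there is one, comes from routine clinical decisions. Set side by side, the two do not measure the same thing.

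The formula also assumes that every subject is on PEG-ADA at transplant and stops once afterwards. Neither document says so. Protocol 6.4.1 itself foresees a stop, a restart and a second stop.

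What is at stake is a between-group table or curve that could be read as evidence on freedom from PEG-ADA, which it cannot supply.

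**Working it through.** The plan gives no sample size, power or expected value for this endpoint, so there is no stated figure to reproduce. The check puts values into the SAP's own formula.

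**Inputs.** Scheduled stop: day +30 (Protocol 7.4 and 6.4.1). Formula: 12 x (stop day − transplant day)/365.25 (SAP 8.3.3.1). Controls identified: 25 at GOSH and 10 at Duke, so 25 + 10 = 35 (Protocol Appendix H). All other days below are illustrations.

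**Step 1: OTL-101, stopped to schedule.** 12 x 30/365.25 = 0.986, or 0.99 months. A poor graft and a good graft give the same number. A stop deferred to day 60 gives 12 x 60/365.25 = 1.97 months, and to day 90 gives 2.96 months. Such a spread would reflect infection or medical status at day 30, not ADA correction.

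**Step 2: stopped before transplant.**

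| Days before transplant | Time by the formula (months) |
|---|---|
| 30 | −0.99 |
| 90 | −2.96 |
| 365 | −11.99 |

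Negative times cannot be placed on a curve that starts at transplant. In a mean or median they would sit among the positive values.

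**Step 3: never on PEG-ADA.** There is no stop date, so there is no value. The child is not still receiving PEG-ADA either, so the censoring rule does not apply. This can occur in either group.

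**Step 4: stop at day 30, restart at day 200** (12 x 200/365.25 = 6.57 months). The SAP does not say which stop date counts. If it is the first, the child scores 0.99 months. If a later re-stop counts, the child scores that date. If the child is regarded as still receiving, the child is censored at the last visit. All three fit the text.

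**Step 5: how many controls.** SAP 8.2.16 lists ERT before and after transplant as things to count, so the plan does not take it that all controls were on ERT throughout. It does not say how many were not. As pure illustration, a share of 10% to 50% would be 35 x 0.10 = 3.5 to 35 x 0.50 = 17.5 controls without a positive time. Nothing in the documents supports a particular share.

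**Step 6: direction.** If pre-transplant stoppers and never-users are dropped from the curve, only controls still on ERT after HSCT remain, which makes OTL-101 look quicker. If negative times stay in the descriptive statistics, they pull the control summary down and make HSCT look quicker. A control who stops on the day of transplant scores 0, ahead of the 0.99 months scheduled for OTL-101. The sign of any distortion is therefore not determined.

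**The case against.** The strongest reply is that nothing rests on this summary. It is an additional endpoint, absent from the endpoint lists in Protocol 4.2.2 and 11.3.3 and SAP 5.2. SAP 6 names overall survival, event-free survival, IgRT use and infection rate as the HSCT comparisons for the primary and final analyses. No test is attached, and the curve is optional. Restarts are already events in event-free survival. All of this stands, and it keeps the point minor.

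A reader might infer that the SAP counts failures as early successes. The text does not establish that: it holds only if the stop date means the first stop, and a restarted child may equally be censored as still receiving.

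A reader might also set the IgRT section against this one, because it contains the condition "without restarting at any subsequent time point". That condition applies to the number (%) off IgRT at 12, 18 and 24 months. The IgRT time formula uses a single stop date and the same kind of censoring as the PEG-ADA formula, so the SAP is not stricter on time for IgRT. The useful precedent is the proportion.

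It can also be said that event-free survival makes a replacement unnecessary. That is only partly right. A child in either group who never stops PEG-ADA has no reinstitution and is not an event on that ground. A child who first starts ERT after transplant is not clearly one either.

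**Conclusion.** The point holds as a minor one. For children managed to schedule, the OTL-101 value is about 0.99 months by design, so it does not measure efficacy, and a between-group summary of it does not show who is free of PEG-ADA. The formula is undefined for never-users, negative for pre-transplant stoppers and ambiguous for restarts. These conclusions follow from the text and need no assumption about the controls.

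Three stronger readings are not supported. The first is that every OTL-101 value equals day +30: the stop is conditional, so later values can occur. The second is that the comparison is biased towards OTL-101: the direction depends on handling that the SAP leaves open. The third is that most controls would drop out of the curve: the documents give no share. The primary and key secondary analyses are unaffected.

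**What to change.** For the between-group summary in SAP 8.3.3.1, report the number (%) in each group alive and off PEG-ADA at 12 and 24 months with no restart up to that time, in a form similar to the IgRT proportion in SAP 8.3.2.2. Count never-users and pre-transplant stoppers as off from transplant. Count continued use, restart, first start after transplant, rescue transplant or death as not achieved. Keep time to PEG-ADA stop for OTL-101 only, labelled as a description of exposure, and state which stop date it uses.

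The cost is SAP wording and one derived variable. Protocol Appendix H already has Duke recording ERT before and after transplant, with the time of any reinitiation. For GOSH it lists only previous ERT and its duration, but the event-free survival comparison and SAP 8.2.16 already need post-transplant ERT status, so its availability should be confirmed there. The time-to-stop comparison with HSCT is lost. The new measure overlaps in part with event-free survival and adds mainly the children who never stop ERT or who first start it after transplant. No clinical rule changes.

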8.3.4 Sensitivity Analyses

Protocol violations in this study will be reviewed prior to database lock in order to determine whether any major violations have occurred that could have influenced the outcome of the study. In the event that such violations have occurred, sensitivity analyses will be carried out in order to assess the impact of these violations on the efficacy results.

Sensitivity analyses will be carried out for:

- Overall and event free survival (descriptive statistics and Kaplan-Meier analyses)
- Lymphocyte subsets (descriptive statistics and plots)
- Measures of engraftment (descriptive statistics and plots)

8.4 Safety Evaluations

8.4.1 Adverse Events

All adverse events will be coded using MedDRA version 20.0

8.4.1.1 Definition of Treatment-emergent Adverse Events

Adverse events (AEs) will be summarised on the basis of treatment emergence. An adverse event is considered to be treatment emergent if it occurred on or after the date and time of the start of the OTL-101 infusion. If the start time of the event is not present, any event starting on the same day as the infusion will be considered to be treatment emergent. If the start date of the adverse event is partial or missing, it will be considered to be treatment emergent if:

- the day is missing, the month and year are present and are the same as or after the month and year of the infusion and the end date is missing or is not before the date of infusion,
- the day and month are missing, the year is present and is the same as or after the year of the infusion and the end date is missing or is not before the date of infusion,

Final Version 4.0 Page 22 of 27

• the entire date is missing and the end date is missing or is not before the date of infusion.

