4.2 Study Endpoints

4.2.1 Primary Endpoints

4.2.1.1 Evaluation of Safety

Primary Endpoint: Incidence and grade of Serious Adverse Events (SAE).

Serious adverse events may be manifest as:

- a) clinical toxicities
- b) exposure to replication-competent lentivirus (RCL)
- c) development of monoclonal expansion or leukoproliferative complications from vector insertional effects.

a) To detect potential clinical toxicities from the treatment, patients will have interval medical histories taken, complete physical examinations, and phlebotomy to obtain peripheral blood for laboratory studies on day +1, and then at months 1, 2, 3, 4, 5, 6, 8, 10, 12, 15, 18, 21 and 24 (+/- 4 weeks). Laboratory studies performed at these time-points will include CBC with differential and platelet count and a chemistry panel and electrolytes. Toxicities relative to the clinical parameters, the CBC with differential, and the chemistry panel are defined by an adapted Pediatric Clinical Toxicity Scale from the NIAID, Division of AIDS. ([Appendix G](#))

Patients will also be monitored by clinical examination and laboratory studies in the immediate period (3 to up to 6 weeks, depending on clinical course) after infusion of OTL-101 to monitor myelosuppression expected from the administered busulfan.

b) To detect exposure to replication-competent lentivirus:

i. PBMC will be assayed by PCR to detect RCL. This test will be performed by the National Gene Vector Biorepository on samples obtained at baseline (pre-infusion), 3, 6, 12 and 24 months post-infusion. Samples will also be collected annually thereafter, and cells archived for PCR assay, to be run if any samples are positive.

ii. Serum for measurement of antibody to RCL will be archived for the presence of antibody to VSV-G envelope at baseline (pre-infusion), 3, 6, 12 and 24 months post-infusion (and annually thereafter).

c) To monitor for monoclonal expansion or leukoproliferative complications, LAM-PCR will be performed, as described in [Appendix F](#).

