8.3 Treatment

If physical exam, blood tests, and urinalysis performed within 3 days of the planned bone marrow harvest meet the inclusion criteria, the subjects will undergo the bone marrow harvest under general anesthesia. A total volume of no greater than 20 mL/kg subject body weight will be collected in order to isolate CD34+ hematopoietic progenitor cells. Subjects who meet criteria to receive Busulfan (enough cells to freeze back-up and to start culture with $\geq 1 \times 10^6$ CD34+ cells/kg) will remain hospitalized after the bone marrow harvest, for busulfan administration.

Busulfan will be administered as a single IV dose (4 mg/kg) over 3 hours approximately 12-24 hours after the bone marrow harvest (See [Appendix C](#) for Schedule for Busulfan Marrow Cytoreduction). Peripheral blood samples will be drawn at the following time-points for busulfan area-under-the curve (AUC) pharmacokinetic studies: immediately following the completion of the infusion; at 0, 1, 2, 4, 8 and 13 hours after the end of the infusion. These labs may be drawn within 15 minutes of the timepoint, but the actual time in reference to the administration of busulfan should be recorded for accurate AUC calculation.

Schedule for Busulfan Marrow Cytoablation

If the gene-modified CD34+ cells meet acceptance criteria at the end of the culturing period, they will be infused intravenously into the subject (approximately 24-48 hours after busulfan administration).

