9.5.2.4 UCLA to RAC

We will follow the *NIH Guidelines* ([Appendix M-I-C-4. Safety Reporting, April 2016](#)) when reporting SUSARs to the RAC.

Any SAE that is both unexpected and associated with the use of the gene transfer product will be reported to the RAC within 15 calendar days after the sponsor's initial receipt of the information.

Any SAE that is fatal or life-threatening, unexpected and associated with use of the gene transfer product will be reported to the RAC within 7 calendar days after the sponsor's initial receipt of the information.

All reportable SAEs will be followed until satisfactory resolution or until the clinical investigator deems the event to be chronic or the participant to be stable.

Anticipated SAEs that are not considered expedited reportable events include:

- Anemia from the bone marrow harvest
- Thrombocytopenia, neutropenia, and elevated liver enzymes from busulfan

All SAEs designated as "not related" to the investigational product under study or to the study intervention and all non-serious AEs will be recorded and reported to the regulatory agencies in the sponsor's annual report to these agencies.

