11.2 Design Considerations and Data

This is a subject-level historically controlled, prospective, non-randomized Phase I/II clinical trial to assess the safety and efficacy of autologous transplantation of CD34+ cells originated from the bone marrow of ADA-SCID infants and children following human ADA cDNA transfer by the EFS-ADA lentiviral vector.

Descriptive results will be presented for the study cohort.

Comparisons will be made to three cohorts:

- 1) A historical control group consisting of ADA-SCID HSCT-treated subjects lacking a medically eligible HLA-matched sibling/family donor and treated at GOSH/UCL (UK) or Duke University Children's Hospital, North Carolina Transplant Center (USA) from the year 2000 onward
- 2) A historical control group consisting of ADA-SCID HSCT-treated subjects having a medically eligible HLA-matched sibling/family donor and treated at GOSH/UCL (UK) or Duke University Children's Hospital, North Carolina Transplant Center (USA) from the year 2000 onward
- 3) All HSCT-treated subjects from GOSH/UCL or Duke University Children's Hospital, who were treated with HSCT from the year 2000 onward, with any type of donor

Details on the historical HSCT control groups from GOSH/UCL and Duke University Children's Hospital can be found in [Appendix H](#).

Statistical analyses will be performed, and their outcomes presented, in three stages:

- Interim look – 6 months
 - Descriptive statistics for all available subjects
- Primary analysis - Comparison on primary efficacy endpoints to the HSCT control cohorts—12 month follow-up analysis
 - Descriptive statistics for the complete study cohort, with all patients having reached at least 12 month follow-up
 - Comparison to HSCT control cohorts on safety, primary efficacy endpoints and need of immunoglobulin replacement (IgRT) (main secondary efficacy endpoint).
- End of study analysis:
 - Descriptive statistics for the complete study cohort, with all patients having completed the study (24-month follow-up)
 - Comparison to HSCT control cohorts on safety, primary efficacy endpoints and need of immunoglobulin Replacement (IgRT) (main secondary efficacy endpoint).

In each study stage and for all analyses, all relevant data available will be used.

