8.4.1.2 Serious Adverse Events

The primary safety parameter in this study is the incidence and severity of serious adverse events (SAEs).

Incidence and frequency of treatment emergent SAEs will be summarised by system organ class (SOC) and preferred term (PT):

- overall,
- by maximum severity,
- by maximum relationship to treatment
- treatment related SAEs.

In each table, if the same SOC or PT is reported on multiple occasions for a single subject, it will be included only once in the summary. In the table by maximum severity, only the most severe occurrence for each SOC and PT for each subject will be included in the summary. In the table by relationship, only the most related occurrence for each SOC and PT for each subject will be included in the summary.

Any SAEs that are not treatment emergent (occurred prior to the infusion) will be listed.

If there are any deaths, the details will be listed.

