10.1 Changes in Version 3.0

Since Statistical Analysis Plan version 2.0 was signed off on 14th March, 2017, Version 10.0 of the protocol has been signed off, so a number of modifications were needed to this SAP in order to account for the changes in the protocol.

In addition to these changes, the document has been restructured in order to improve the flow and the understandability. In particular, the description of any derivations of the endpoints has been added to the statistical methods section instead of being with the list of endpoints. Also, some of the details relating to programming specifications have been removed and will be added to the programming documentation.

Changes of note are:

- Study objectives and endpoints have been reworded to match protocol version 10.0.
- The age at entry and transplant will be expressed in months rather than years as this is more appropriate for the subjects enrolled.
- The calculation of durations in months has been changed from days/30 to 12*days/365.25 to be consistent with calculations of age.
- Inclusion/exclusion criteria will no longer be summarized, but will be listed.
- A summary of the busulfan AUC has been added.
- The plots of parameters over time will no longer present the mean +/- 2SE, but the median and range as this was more appropriate for the parameters being presented.
- The infection summaries have been reworded to match the definition of severe infections from the protocol.
- Additional adverse event summaries have been added and it has been explicitly stated that all summaries will only include treatment emergent adverse events.
- Summaries of laboratory evaluations using descriptive statistics have been added.
- Plots of vital signs over time have been removed as they were not considered to be useful.
- Plots of antibody responses over time and summaries by visit have been removed as the data will not be collected over time for individual subjects.

Final Version 4.0 Page 26 of 27

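### SAEs that start between the first study harvest and the OTL-101 infusion are listed but left out of the primary safety tables, and the treatment-emergence rule gives no anchor for the HSCT controls

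*SAP*

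**What the plan says.** **Treatment emergence.** SAP 8.4.1.1 treats an event as "treatment emergent if it occurred on or after the date and time of the start of the OTL-101 infusion". Its extra rules for missing times and partial dates all refer to that same infusion. No other starting point is given.

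**The tables.** SAP 8.4.1.2 names SAE incidence and severity as the primary safety parameter, then says: "Incidence and frequency of treatment emergent SAEs will be summarised by system organ class (SOC) and preferred term (PT"). There is one such table for all SAEs, one by worst severity, one by closest relationship, and one limited to treatment-related SAEs. For everything earlier it says: "Any SAEs that are not treatment emergent (occurred prior to the infusion) will be listed". SAP 8.4.1.3 follows the same pattern for all AEs. The change record in SAP 10.1 shows that the restriction was intended: "it has been explicitly stated that all summaries will only include treatment emergent adverse events".

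**The endpoint.** Protocol 4.2.1.1 states "Primary Endpoint: Incidence and grade of Serious Adverse Events (SAE") without saying that counting begins at infusion. The objective in Protocol 3.1 is the safety of the autologous transplantation.

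**The sequence.** Protocol 8.3 says: "Busulfan will be administered as a single IV dose (4 mg/kg) over 3 hours approximately 12-24 hours after the bone marrow harvest". It places the cell infusion roughly 24 to 48 hours after busulfan. Among the anticipated SAEs that Protocol 9.5.2.4 exempts from expedited reporting is "Anemia from the bone marrow harvest".

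**The controls.** SAP 7.2 puts the complete HSCT cohort in the safety population, and the opening of SAP 8 has the controls shown by donor group in all summaries. Protocol 11.2 plans, at the 12-month and end-of-study analyses, a "Comparison to HSCT control cohorts on safety, primary efficacy endpoints" and need for immunoglobulin replacement. Protocol 11.6.2.3 plans descriptive safety by arm.

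**The concern.** No subject receives OTL-101 without a harvest under general anaesthesia and a dose of busulfan first. Protocol 2.3.1 describes both as study risks: it mentions rare death under anaesthesia, and it says the toxicity of low-dose busulfan in children is not known. A reader of the primary SAE table will take it as the SAE rate of the whole procedure. As specified, it is the rate from infusion onward, so an anaesthetic complication or an acute busulfan reaction would not be in it.

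The control problem is different. Controls never receive OTL-101, so the rule gives them no date to count from. The tables are due to show a control column, and the plan does not say how to fill it. An analyst would have to choose a start point after the data are in hand.

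**Working it through.** The point concerns a definition, and the plan states no figure to reproduce. The check measures the excluded window from the protocol's own timings and then applies the rule literally.

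**Length of the window**

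- Harvest to busulfan: about 12 to 24 h (Protocol 8.3).
- Busulfan to infusion: about 24 to 48 h (Protocol 8.3).
- Harvest to infusion: 12 + 24 = 36 h at the short end and 24 + 48 = 72 h at the long end.
- If the 24 to 48 h is counted from the end of the 3 h busulfan infusion: 36 + 3 = 39 h to 72 + 3 = 75 h.
- The part that follows the start of busulfan: 24 to 48 h, or 27 to 51 h on the second count.
- Optional back-up harvest in patients over 2 years (Protocol 7.3): about 1 to 3 months before gene transfer.
- Second harvest after a low first yield (Protocol 6.1): at least one month after the first, with no maximum stated.

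**The rule applied to typical events**

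| Event | Treatment emergent? |
|---|---|
| Harvest or anaesthesia SAE, day -2 | No |
| Acute busulfan reaction, day -1 | No |
| Day 0, timed before the infusion | No |
| Day 0, no time recorded | Yes |
| Day missing, same month as infusion, no end date | Yes |
| Busulfan neutropenia, onset day +14 | Yes |
| HSCT control event with a full or partial start date | No (no OTL-101 infusion exists) |
| HSCT control event with no start and no end date | Yes, by the last bullet of SAP 8.4.1.1 |

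**Effect on the primary figure.** SAP 2 gives 19 + 1 = 20 treated subjects. A subject with an SAE before infusion and none afterwards moves from counted to uncounted: 1/20 = 5 percentage points. A subject who also has an SAE after infusion stays in the overall incidence, but loses the earlier event from the tables by preferred term, severity and relatedness. The documents give no count of pre-infusion SAEs, so the total effect is not known.

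**Whether the control anchor is supplied elsewhere.** For survival, event-free survival, IgRT and PEG-ADA (SAP 8.3.1.1, 8.3.1.2, 8.3.2.2 and 8.3.3.1), the SAP counts from transplant and gives an age-based substitute where control dates are not recorded. SAP 8.4.1 has no counterpart. Protocol Appendix H collects age at transplant for the Duke controls, so a rule based on date and time could not be applied to them directly.

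**The case against.** There is a reasonable case for the infusion as anchor. Protocol 9.2 defines an AE by its timing relative to the investigational agent, Protocol 6 defines that agent as the transduced cells, and Protocol 9.4.1 schedules AE assessment after infusion. Safety is descriptive, there are 20 subjects, and every earlier SAE is to be listed, so a careful reader could find each one. For the controls, the comparisons named in SAP 6 are survival, IgRT and infection rate (with demographics and survival at the interim look), not AEs. The infection rate is already split at 12 months after transplant, and Duke SAEs are collected as changes after HSCT. Most analysts would take the transplant date or age as the control anchor without being told.

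Much of this stands. The events are displaced, not lost, and the control gap taken alone is close to a missing detail. It does not remove the main point. The protocol counts harvest anaemia among anticipated SAEs, so its own SAE concept reaches back before the infusion, and a listing does not enter an incidence.

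Some stronger readings are tempting and are not supported:

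- **That busulfan toxicity as a class leaves the tables.** Protocol 4.2.1.1 monitors myelosuppression for 3 to 6 weeks after the infusion, and onsets in that period are tabulated. Only reactions that start before the infusion are excluded.
- **That harvest anaemia can never be counted.** The test is onset, not cause. Anaemia recorded with onset on or after infusion is included.
- **That no control event could ever qualify.** An event with neither start nor end date does, by the missing-date rule.
- **That two or three days are always lost.** The short end of the window is about a day and a half.

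**Conclusion.** The point holds in this limited form. The primary SAE tables are narrower than the protocol's primary safety endpoint. They omit SAEs with onset between the first study harvest and the infusion, which in practice means harvest and anaesthesia events and acute busulfan reactions. Followed exactly, the rule understates SAE incidence whenever a subject's only SAE falls in that window. Whether any subject is in that position cannot be told from the documents.

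The missing control anchor is a secondary gap. It matters because control safety summaries are required, but one sentence closes it.

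The conclusion rests on two assumptions: that the protocol's endpoint, which states no start, covers the whole transplant procedure named in the objective, and that the protocol's approximate intervals describe what was done.

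**What to change.** 1. **OTL-101 subjects.** Tabulate SAEs and AEs from the first study harvest, including any separate back-up harvest, in three columns: pre-infusion, post-infusion and total. The post-infusion column is the table now planned, so nothing is given up.
2. **Comparison with controls.** Count events in both groups from the transplant infusion, OTL-101 or HSCT. Where control dates are not recorded, use age at event minus age at transplant, following the approach of SAP 8.3.1.1, and count a difference of zero or more. Ages in months cannot order two events in the same month, so state how ties are handled. Counting them as post-transplant would match the SAP's treatment of same-day events without a time.
3. **Data check before lock.** The planned listings imply that pre-infusion events are recorded. Confirm that this extends back to early back-up and first harvests, and that the timing of control events was captured, since Appendix H does not say so for each event.

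The cost is SAP wording, the extra columns and a reported SAE rate that may be slightly higher. No clinical procedure changes.
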